3.6.1. Primary Data Collection

Primary data collection forms will be made available electronically (as fillable PDF documents or online forms), but may also be provided/completed in hard copy to suit the unique needs of each participating research site and participant visit. Where necessary, participants will have the option to have data collection forms mailed to them with pre-paid return envelopes to the research site or SCC. Thus, questionnaires can be completed at-home by participants, in-person during a scheduled study visit, or over the telephone with the Investigator/Delegate, as needed.

The primary data collection schedule is summarized in Table 1.

Table 1. Primary Data collection schedule for vaccinated participants

	Enrollment	Post-vaccination Follow-up ¹				
		RQ1 and RQ2	V2	V3	V4	V5
Baseline Questionnaire	X					
Reactogenicity Questionnaire		X				
General Follow-up Questionnaire			X	X	X	X

¹Post-vaccination follow-up may occur or extend into the postpartum period depending on when participants enroll into the study.

[figure not shown]
- If participant is getting a 2-dose vaccine, and dose 2 scheduling is delayed (for any reason – federal/provincial/local recommendations, participant reasons), data and sample collection will be done every 3 months until dose 2 is administered.
- Baseline questionnaire must be completed prior to or at V2.
- General questionnaires must be completed prior to or at following study visit.
- RQ1 must be completed prior to 2nd dose.
- RQ2 must be completed within 30 days after last dose (for single vaccine or second dose)*
- If participant is getting a 2-dose vaccine, and dose 2 scheduling is delayed (for any reason – federal/provincial/local recommendations, participant reasons), data and sample collection will be done every 3 months until dose 2 is administered.

Baseline questionnaire

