A baseline questionnaire will be administered **at enrollment** to document participant characteristics. We will collect socio-demographic information (e.g., maternal age, ethnicity, occupation, education, household income), medical and obstetrical histories (e.g., parity, pre-existing conditions), receipt of blood products or other vaccines in pregnancy, other lifestyle risks (e.g., tobacco, alcohol and other substance use), and previous SARS-CoV-2 infection history. Key factors influencing participant decision-making to receive the COVID-19 vaccine (decision needs, information access, family and societal pressures) will be documented.

Reactogenicity questionnaires

After each COVID-19 vaccine dose we will collect priority variables for studying COVID-19 vaccination in the maternal-newborn population¹¹:

- **COVID-19 vaccine data:** vaccine product (e.g., Moderna, Pfizer-BioNTech, Janssen (Johnson & Johnson), Oxford-AstraZeneca, etc.), dose number (one or two) and date received (to calculate timing of exposure in pregnancy or postpartum relative to delivery, and length of time between doses, if applicable). Scheduled dates of second COVID-19 vaccine doses (if applicable) will also be collected.
- **Reactogenicity:** injection site (e.g., bruising, swelling, pain) and systemic (e.g., fever, headache, muscle ache, fatigue) reactogenicity since the participant received the most recent vaccine dose.

General follow-up questionnaires

At each subsequent follow-up timepoint:

- **If the participant is still pregnant:** We will ask about significant changes in maternal and fetal health (e.g., new medical diagnoses or illnesses), maternal receipt of any blood products or other vaccinations, and any new maternal COVID-19 diagnoses (including variant information if known) since the last study visit.
- **If the participant is postpartum:** We will ask about significant changes in maternal and infant health (e.g., new medical diagnoses or illnesses), receipt of any blood products or other vaccinations (mother or infant), infant feeding method (e.g., mother's own breastmilk/chestmilk, donor milk, formula, other, combination) and infant growth (e.g., weight, length). We will also ask about any new maternal or infant COVID-19 diagnoses (including variant information if known) since the last study visit.

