- **Stop the Spread Ottawa (SSO) participants:** Non-pregnant females of reproductive age without known history of SARS-CoV-2 infection who received at least one COVID-19 vaccine dose. SSO is an ongoing Ottawa-based, 1000-person prospective cohort study designed to investigate the SARS-CoV-2-specific immune response on COVID-19 convalescent and COVID-19 vaccinated individuals. A total of 126 non-pregnant individuals of reproductive age who have received a COVID-19 vaccine have been enrolled to date. Participants provide monthly blood samples post-vaccination using the same protocols described for the PLAN-V study protocol and are followed for 10 months, allowing for comparison across the PLAN-V time points.

Exposures: The exposure of interest is maternal COVID-19 vaccination in pregnancy (PLAN-V Study) or while not pregnant (SSO Study)

Outcome Measures: The primary immunological outcome measure will be antibody titres acquired from COVID-19 vaccination in pregnant women/individuals will be compared to those of non-pregnant women/individuals. Secondary outcomes will include vaccine reactogenicity, as well as nature and frequency of vaccine-related adverse events.

Sample analysis. Blood serum samples will be evaluated for SARS CoV-2 specific antibodies and neutralizing antibody titres, as well as antibody subclass distributions where appropriate. Samples will be analyzed using the methods described in Section 3.7.3.

Data Sources: Immunogenicity data (including seroconversion rates and antibody titres), vaccine-related data (including product information, reactogenicity and adverse events), and participant characteristics (including sociodemographics, health behaviour risks and medical history) will come from the PLAN-V and the SSO study datasets. The PLAN-V and SSO datasets are both stored at the OHRI, and data elements are aligned thereby facilitating robust comparison of outcome measures.

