4. STATISTICAL ANALYSIS

Descriptive summary statistics will be presented for the study sample, and will include sociodemographic information, obstetrical histories and delivery details. Data will be summarized using frequency distributions for categorical variables, means and medians for continuous variables. A sex and gender-based analysis plus (GBA+) framework will be applied throughout to investigate both sex and gendered related aspects of vaccination among pregnant and their infants including, social and geographic position, race, age, sexuality, sex and gender.

Relative antibody levels will be reported on all positive tests as geometric mean (GM) and their 2-sided 95% confidence intervals (CIs). The maternal response to vaccination will be determined by anti-SARS-CoV-2 antibody levels in maternal serum. Antibody GM with 95% CIs will be compared across time points and between study groups for each sample type. The contribution of IgG subclasses to the total SARS-CoV-2 antibody response will also be reported. Extent and duration of antibody transfer to breastmilk/chestmilk will be evaluated. Infant antibody titres will also be examined to investigate the extent and duration of passive immunity conferred through antibody transfer via the placenta or breastmilk/chestmilk, if any.

Cytokine data will be correlated to detected antibody isotype titres to identify integrated, multi-factorial maternal and newborn immune response signatures to COVID-19 vaccination.

We will account for timing of maternal vaccination in pregnancy/postpartum, vaccine product, number of vaccine doses, COVID-19 infection history, and receipt of other vaccines (mother/child) within the study follow-up period in all analyses.

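### The interval between doses is collected but not among the factors accounted for, so in Objective 4 a difference in dose spacing could appear as a pregnancy effect in post-dose-2 titres

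*Protocol*

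**What the plan says.** Section 4 (Statistical Analysis) names the factors to be handled in all analyses: "We will account for timing of maternal vaccination in pregnancy/postpartum, vaccine product, number of vaccine doses, COVID-19 infection history", followed by other vaccines received by mother or child during follow-up. The interval between doses is not named there, and no other section adds it.

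Section 3.6.1, under the reactogenicity questionnaires, records the date of each dose for two separate purposes: "to calculate timing of exposure in pregnancy or postpartum relative to delivery, and length of time between doses, if applicable". It places these among the study's priority variables. The same section, and the notes to Table 2 in Section 3.7.1, set out what happens if "dose 2 scheduling is delayed (for any reason": data and samples are then collected about every three months until the second dose is given. The interval may therefore vary by months.

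The Objective 4 (SSO) sub-study states as its primary outcome that "antibody titres acquired from COVID-19 vaccination in pregnant women/individuals will be compared to those of non-pregnant women/individuals". It is described as a retrospective analysis of data from two studies. Both groups need at least one dose and no known infection history. No matching or restriction on dosing interval is stated. The SSO vaccine data it names are product, reactogenicity and adverse events; dose dates are not mentioned.

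**The concern.** Of the two quantities that Section 3.6.1 derives from dose dates, timing in pregnancy is carried into the Section 4 list and the interval is not. If dose spacing affects titre and the two cohorts have a different mix of spacings, an analysis that follows Section 4 as written would attribute part of that difference to pregnancy. It could produce an apparent effect or hide a real one. Titre is the primary outcome of Objective 4 and group membership is not randomised, so only restriction, matching or adjustment can deal with this, and none of the three is stated for the interval.

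**Working it through.** **1. Does a listed factor already cover the interval?**

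- Number of doses: no. Two doses weeks apart and two doses months apart both count as two.
- Vaccine product, infection history and other vaccines: none of these records spacing.
- Timing in pregnancy: within PLAN-V it can. With g1 and g2 as gestational age at doses 1 and 2, the interval is g2 − g1, so entering both determines it. In Objective 4 it cannot, because SSO participants are not pregnant and have no g1 or g2.

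The gap is therefore clear in Objective 4 and depends on the model in the main cohort.

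**2. Which samples are affected?** Only those taken after dose 2: Visit 3 onward in two-dose participants, and delivery samples taken after dose 2. At Visit 2 and in one-dose participants the interval is undefined.

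**3. The plan's own figures.** Section 5 gives 93% to 95% power for 95% versus 80% seroconversion with 150 PLAN-V participants. Using a two-sided 0.05 test of two proportions with pooled variance:

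- against 100 COPE dyads: 94.3% to 94.7% (91.5% to 92.3% with continuity correction);
- against 126 SSO participants: 96.7% (95.0% to 95.2% with continuity correction).

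The stated range is reproduced to within 2 points, and this concern does not alter it. Section 5 also gives a detectable geometric mean (GM) ratio of 1.19, without an SD or a power, so that figure cannot be reproduced.

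**4. Size of a spurious ratio.** Assumptions not in the protocol: R is the GM titre ratio of long to short interval, and d is the difference between cohorts in the share with a long interval. With mean log titre = a + β·(pregnant) + ln(R)·(long interval), the unadjusted difference is β + d·ln(R). If pregnancy has no effect (β = 0), the observed GM ratio is R^d, or its inverse if SSO has the longer intervals.

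| R | d = 0.25 | d = 0.50 | d at which R^d = 1.19 |
|---|---|---|---|
| 1 (no effect) | 1.00 | 1.00 | never |
| 1.25 | 1.06 | 1.12 | 0.174/0.223 = 0.78 |
| 1.5 | 1.11 | 1.22 | 0.174/0.405 = 0.43 |
| 2 | 1.19 | 1.41 | 0.174/0.693 = 0.25 |

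The last column is ln(1.19)/ln(R).

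**5. False-positive rate.** Assume further that 1.19 was set at 80% power for 150 versus 126, all with post-dose-2 samples. The implied SD of ln titre is 0.174 / [(1.960 + 0.842) × √(1/150 + 1/126)] = 0.174 / (2.802 × 0.1208) = 0.51, and the standard error is about 0.062. With no pregnancy effect and d = 0.25, the chance of a significant result is about 15% (R = 1.25), 37% (R = 1.5) or 80% (R = 2), against a nominal 5%. The 80% follows by construction, since 2^0.25 = 1.19.

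**The case against.** The strongest reply is that Section 4 is short, does not say that only these factors will be used, and leaves the full covariate set to an analysis plan that is not shown. Since dose dates are collected, nothing prevents the interval from being used. It is true that the list is not declared closed. But the protocol chose to name the factors for all analyses and, of two quantities it derives from the same dates, named one. The point concerns what the stated list leaves out.

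A reader might also infer more than the documents support:

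- **That second-dose delays are expected.** The text is conditional; it makes provision for a delay and does not predict one.
- **That the cohorts are known to differ in spacing.** No interval distribution is given for either. The policy change in the Background concerns priority status and proof of counselling, not dose spacing. SSO is ongoing, and PLAN-V may enrol women who already had a first dose (Section 3.2.1), so a separation in calendar time is not established either.
- **That the main-cohort question on timing and antibody transfer is confounded by interval.** This fails if the timing of both doses is entered, and Section 4 does not restrict timing to one dose.
- **That all of Objective 4 is affected.** Only post-dose-2 samples are.

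Finally, no passage says that interval changes titre. With R = 1 there is no bias, and with R = 1.25 a 78-point difference in long-interval share is needed to reach 1.19. The arithmetic shows what is possible, not what is likely.

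**Conclusion.** The point holds in a limited form. The interval is collected, its variation is provided for, and it is missing from the factors in Section 4. In Objective 4 nothing listed takes its place, so the post-dose-2 titre comparison is open to confounding by dose spacing. Whether bias occurs, in which direction and how large it would be cannot be determined from the protocol; the illustrative ratios of 1.06 to 1.41 rest on assumed values of R from 1.25 to 2 and d of 0.25 or 0.50. What the illustration does show is that a comparison meant to detect a ratio as small as 1.19 could be sensitive to a moderate imbalance if interval matters. This is worth correcting before analysis; it does not invalidate the design or change any stated sample size or power figure.

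**What to change.** In Section 4, add the interval between dose 1 and dose 2 as an adjustment covariate for analyses of post-dose-2 samples, above all the PLAN-V versus SSO titre comparison. Report the interval distribution in both cohorts and the extent of overlap, so that a reader can see how far the adjusted comparison rests on the model. Confirm that the SSO dataset holds dose dates: the sub-study text says that data elements are aligned but does not name them.

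The cost in PLAN-V is one variable that is already collected. Some precision will be lost if the intervals overlap little, and the overlap report would make that visible. Matching or analysis within interval bands is not required; with about 150 and 126 participants either could cost more precision than covariate adjustment, and that loss has not been estimated. No visit or dosing schedule needs to change.

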Sample analysis. Maternal and newborn cord blood serum samples collected at the time of delivery will be evaluated for SARS CoV-2 specific IgG and neutralizing antibody titres and IgG subclass distribution. Samples will be analyzed using the methods described in Section 3.7.3.

Data Sources: Immunogenicity data (including seroconversion rates and antibody titres), and data on participant characteristics (including sociodemographic information and pregnancy, delivery and newborn outcomes), will be obtained from the PLAN-V and COPE Network study datasets. The PLAN-V dataset has been purposefully aligned with that of the COPE Network Study thereby facilitating robust comparison of antibody and health outcome data. The COPE Network Study dataset includes comprehensive information on SARS-CoV-2 infection (date and gestational age of diagnosis, virus titres, symptomology, maternal and newborn case management) derived from the Ontario provincial birth registry, BORN Ontario, which has province-wide data collection on COVID-19 infection in pregnancy. The PLAN-V study data will be transferred to BORN for analysis.

Objective 4: SSO Sub-study

Comparing immune responses to COVID-19 vaccination between pregnant and non-pregnant women/individuals

Study design: A retrospective analysis of immunological data generated from two research studies

Study Population: We will use samples collected from mothers who were enrolled in the current PLAN-V study and the *Stop the Spread Ottawa (SSO)* study (OHSN: 20200481-01H; uOttawa: H-09-20-6135).³

[figure not shown]
- **PLAN-V study participants:** Women/Individuals who received at least one COVID-19 vaccine dose in pregnancy (any type). We will limit this analysis to women/individuals without known history of SARS-CoV-2 infection, and for whom maternal blood samples were collected.

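### For the pregnant versus non-pregnant comparison (Objective 4), the covariates that Section 4 commits to give little control of confounding, and maternal age, medical history and health behaviours have no stated adjusting role

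*Protocol*

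**What the plan says.** Section 4 states the analysis of antibody levels in one line: "Antibody GM with 95% CIs will be compared across time points and between study groups for each sample type". It names no regression model, matching, weighting or standardisation on participant characteristics.

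It then makes one commitment on covariates: "We will account for timing of maternal vaccination in pregnancy/postpartum, vaccine product, number of vaccine doses, COVID-19 infection history", followed by "receipt of other vaccines (mother/child) within the study follow-up period in all analyses". Age appears elsewhere in Section 4 only under the GBA+ framework, among the aspects to be investigated: "including, social and geographic position, race, age, sexuality, sex and gender".

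Two objectives set PLAN-V against an outside cohort. Objective 4 uses SSO (non-pregnant, vaccinated) and Objective 3 uses the COPE Network study (infected in pregnancy). Section 3.4.1 lists both comparisons among the primary outcomes.

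On the data held:
- PLAN-V baseline questionnaire (Section 3.6.1): "socio-demographic information (e.g., maternal age, ethnicity, occupation, education, household income), medical and obstetrical histories". Pre-existing conditions and tobacco use are also collected.
- Objective 4, Data Sources: "participant characteristics (including sociodemographics, health behaviour risks and medical history) will come from the PLAN-V and the SSO study datasets". The data elements are described as aligned.
- Objective 3, Data Sources: "data on participant characteristics (including sociodemographic information and pregnancy, delivery and newborn outcomes", from PLAN-V and COPE. Medical history and smoking are not named.

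**The concern.** The Objective 4 cohorts were recruited separately, one through Ontario obstetric sites and the other through an Ottawa cohort study of convalescent and vaccinated people. They may differ in age, health and behaviour as well as in pregnancy. If such a characteristic affects titre and differs between the cohorts, an unadjusted GM ratio mixes its effect with that of pregnancy.

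This is more than detail left for later. The protocol fixes a covariate list for every analysis, and that list contains vaccine and infection factors only. An analyst who follows it exactly produces a cohort contrast with no adjustment for any characteristic of the woman, although the protocol says the data are available. If confounders are chosen only after the titres are seen, a comparison listed as a primary outcome is open to discretion.

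**Working it through.** **1. The plan's own figure.** Section 5 states 93% to 95% power for 95% versus 80% seroconversion with 150 PLAN-V participants. The comparison sizes are taken from the sub-study sections: 126 for SSO and 100 for COPE (stated as more than 100). Two-sided alpha of 0.05 is assumed.

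Power = Φ{[|p1 − p2| − 1.96·√(p̄(1 − p̄)(1/n1 + 1/n2))] / √(p1(1 − p1)/n1 + p2(1 − p2)/n2)}

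- 150 vs 126: p̄ = (142.5 + 100.8)/276 = 0.8815. Then (0.15 − 0.0765)/0.0398 = 1.84, so power is 96.7%.
- 150 vs 100: p̄ = (142.5 + 80)/250 = 0.89. Then (0.15 − 0.0792)/0.0438 = 1.62, so power is 94.7%.

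This reproduces the stated range to within 2 percentage points with a plain two-group calculation and no covariates. The point here disputes no figure in Section 5.

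**2. What each listed covariate can do in the two contrasts.**

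| Listed factor | Objective 4 (PLAN-V vs SSO) | Objective 3 (PLAN-V vs COPE) |
|---|---|---|
| Infection history | No known history in either group, by restriction | None in one group, all in the other: it is the exposure |
| Timing in pregnancy/postpartum | Does not apply to SSO | Vaccination timing does not define the infected group |
| Product, number of doses | Usable, but describe the vaccine, not the woman | Do not define the infected group |
| Other vaccines | Usable | Usable if recorded in COPE |
| Age, medical history, health behaviours | Not listed; stated to be available | Not listed; only sociodemographic data named as shared |

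**3. Possible size, for illustration.** The documents give no ages, no age slope for titres and no comorbidity rates, so every input here is an assumption. If log titre is linear in age with the same slope in both cohorts, a fall of f per decade and a difference of d years in mean age give

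spurious GM ratio = (1 − f)^(d/10).

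| f per decade | d = 0 | d = 3 | d = 5 | d = 8 |
|---|---|---|---|---|
| 5% | 1.00 | 0.985 | 0.975 | 0.960 |
| 10% | 1.00 | 0.969 | 0.949 | 0.919 |
| 20% | 1.00 | 0.935 | 0.894 | 0.837 |

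Which cohort is older is unknown, so the inverse ratios are equally possible. The ratio Section 5 calls detectable is 1.19, or 1/1.19 = 0.840 the other way round. Only the extreme corner reaches it (0.8^0.8 = 0.837).

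For a medical condition that multiplies titre by r and differs in prevalence by Δ, the ratio is r^Δ. It runs from 0.7^0.05 = 0.982 to 0.5^0.20 = 0.871.

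**The case against.** **The list is not closed.** Section 4 does not say that these are the only covariates, and a statistical analysis plan may name more. A reader might infer that the protocol rules out adjustment for age or medical history; the text does not support that. What stands is that these five factors are all the protocol commits to, for every analysis.

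**Age is mentioned.** The GBA+ framework names age and social position and is to apply throughout, so it would be wrong to say that age appears only in baseline tables. But the sentence is about exploring aspects of vaccination among pregnant participants and their infants. It does not adjust a contrast with non-pregnant women.

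**Restriction is partly in place.** SSO is limited to females of reproductive age, which deserves credit. No age bounds are given, PLAN-V enrols from 16 years, and the restriction does nothing for medical history.

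**No causal claim is made.** Objective 4 is worded as a comparison of immune responses. A reader might infer that the protocol will present cohort differences as effects of pregnancy; it does not say so. Even so, the comparison is of interest mainly for what it says about pregnancy.

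**Objective 3 is different.** A reader might carry the whole argument over to COPE. The documents do not support that: both groups were pregnant and are assessed at delivery, nothing suggests a particular age gap, and medical history and smoking are not named as shared data. Only the sociodemographic part carries over.

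**The size is assumed.** This is correct. Section 5 also gives neither an SD nor a power for the 1.19 ratio, so it serves only as a yardstick.

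**Conclusion.** The point holds for Objective 4. The covariates Section 4 commits to leave a non-randomised contrast between two cohorts with little control of confounding, and characteristics described as available in aligned datasets are given no adjusting role. For Objective 3 it holds in a narrower form: infection history is the exposure and cannot be adjusted for, and the sociodemographic variables shared with COPE should be.

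The bias is a risk whose size cannot be determined from the documents. Under the assumed grid with a 3 to 8 year gap, the spurious GM ratio runs from 0.98 to 0.84 or the inverse, and it is 1.00 if mean ages are equal. A reader might take the upper end as the expected error, but the documents support no particular value. SSO age is taken to be held because that group is selected on reproductive age; the protocol names only sociodemographics. The change is worth making because it costs little and the comparison is listed as a primary outcome.

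**What to change.** In Section 4:

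- **Objective 4:** add maternal age (continuous), pre-existing conditions and smoking, where held in both datasets, to the stated adjustment set. Limit SSO to the observed PLAN-V age range. Report the adjusted GM ratio beside the unadjusted one.
- **Objective 3:** state that infection history defines the groups and is not adjusted for. Adjust for maternal age and the other sociodemographic variables shared with COPE. Add medical history or smoking only once they are confirmed to be in the COPE dataset.

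The cost is a few sentences and a check of the SSO and COPE data dictionaries. PLAN-V needs no new data collection. The age limit would lose a small number of the SSO women, of whom 126 were enrolled when the protocol was written.
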